#### Patient's Global Assessment of Disease Severity Scale

Clear	No psoriasis symptoms at all
Very mild	Very slight psoriasis symptoms, does not interfere with daily life
Mild	Slight psoriasis symptoms, interferes with daily life only occasionally
Moderate	Definite psoriasis symptoms, interferes with daily life frequently
Severe	Intense psoriasis symptoms, interferes or restricts daily life very frequently

*Note: Subjects with disease severity classified as "Clear" or "Very Mild" disease after the treatment period will be rated as having "Controlled disease".*

#### **Patient's Assessment of Itch and Sleep**

At SV2 and Visits 1 to 5 and early withdrawal (if applicable), subjects will complete the itch and sleep questionnaire consisting of three questions ([Appendix V](#)). Subjects will be asked to rate the intensity of their itch and sleep loss during the last 24 hours by marking a line on the scale.

#### **10.8.3.3 Imaging Assessments**

Not Applicable

#### **10.8.4 Laboratory Assessments**

##### **10.8.4.1 Central Analysis**

Samples for analysis of the parameters listed below will be taken as scheduled in the flowchart (cf. 10.8.1) or at early withdrawal from the treatment period of the study.

It is recommended that indwelling catheters introduced under topical anaesthesia are used for the repeated blood sampling, to minimise discomfort for the subject, unless the (sub)investigator judges that there are reasons for not doing it.

A 6.5 ml sample of venous blood and a 30 ml spot urine sample will be taken at SV2, Visit 3 and Visit 5. The 6.5 ml sample of blood will consist of 2 ml for haematology analysis, 2.5 ml for serum biochemistry analysis and 2 ml for analysis of plasma parathyroid hormone. The samples will be taken before the ACTH-challenge test that is also scheduled for these visits (for U.S. only). Measurement of serum cortisol concentration will be included in the biochemistry analysis, and this value will be the baseline serum cortisol concentration for the ACTH-challenge test.

At Visit 3, a 12mL (2 x 6 mL) blood sample will be taken for pharmacokinetic analysis.

Prior to SV2, Visit 3 and Visit 5, subjects will collect 24 hour urine. It is allowed to collect the 24-hour urinary sample up to three days prior to the study visit.

The Central Laboratory will provide the materials and instructions necessary for the collection and transport of the samples.

The following analyses will be performed on the blood samples:

Haematology

Haemoglobin

Haematocrit

Red blood cell (RBC) count

Mean corpuscular volume (MCV)

White blood cell (WBC) count, including differential count

Platelet count

Serum/plasma Biochemistry

Cortisol

Urea

Creatinine

Albumin  
Sodium  
Potassium  
Chloride  
Calcium  
Phosphate  
Parathyroid hormone (plasma)

#### Urinalysis

The following will be analysed quantitatively in the collected 24 hour urine:

Calcium  
Phosphate  
Creatinine  
Volume

The following analyses will be performed on the spot urine sample by dipstick test:

Glucose  
Ketones

The laboratory will also report:

Albumin-corrected serum calcium in mmol/l using the formula:

$$\text{serum calcium (total) in mmol/l} + (0.02 \times [40\text{-serum albumin in g/l] )$$

For the 24 hour urine sample the following will be calculated:

Total calcium excretion  
Total phosphate excretion  
Total creatinine excretion  
Calcium: creatinine ratio  
Phosphate: creatinine ratio

If any laboratory results are abnormal, the (sub)investigator should follow-up the subject as clinically appropriate.

#### Pharmacokinetic Analysis

A 12 mL (2 x 6mL) blood sample for PK analysis will be collected Visit 3 prior to the application of investigational product on the date of the visit.

A blood sample (2 x 6mL) for pharmacokinetic evaluation will be drawn at Visit 3 (4 weeks of treatment) prior to the application of LEO 80185 on the day of the visit. Validated bioanalytical assays will be used for quantification of calcipotriol, betamethasone dipropionate and the metabolites MC1080 and betamethasone 17-propionate in the plasma sample. Full details for taking, storing and shipping the samples for PK analysis will be provided separately.

#### ACTH Challenge test

The ACTH-challenge test will be performed at SV2, Visit 3 and Visit 5. If the subject withdraws prior to completing treatment, the ACTH-challenge test should *not* be performed at early withdrawal.

If the result of the ACTH-challenge test at Visit 3 or Visit 5 shows a serum cortisol concentration  $\leq 18$  mcg/dl at 30 minutes after the ACTH-challenge, a further ACTH-challenge test is required 28 days later at visit FU2. If the results of the ACTH-challenge test at Visit FU2 continue to show a serum cortisol concentration  $\leq 18$ mcg/dl at 30 minutes after ACTH-challenge, further ACTH-challenge tests should be performed, but not more often than at 4-weekly intervals, until the adrenal suppression resolves (i.e., serum cortisol concentration  $> 18$ mcg/dl at 30 minutes after the ACTH-challenge).

The following procedures should be performed prior to the ACTH-challenge tests at SV2 and Visit 3 and 5: Blood pressure/heart rate measurement, blood/urine sampling for central laboratory analysis (haematology/biochemistry/urinalysis) and urine pregnancy test (in female subjects of child-bearing potential).

To perform the ACTH-challenge test, a 2.5 ml sample of venous blood will be drawn at 08.00 a.m.  $\pm 30$  minutes. This sample is also the one on which the biochemistry analyses are performed, as detailed above. After this, CORTROSYN® is injected, as described in Section 10.7. Two further 2.5 ml samples of venous blood will be drawn exactly 30 and 60 minutes after the injection (counting from the end of the period over which the injection is given). Serum cortisol concentrations will be determined for each blood sample by the Central Laboratory.

The time of injection and of blood sampling will be recorded in the CRF.

The following blood volumes will be drawn per subject performing HPA axis assessments:  
6 ml for Haematology;

13.5 ml for Biochemistry

15 ml for ACTH challenge testing

12 ml for PK analysis

Total amount of blood drawn per subject, for central analysis: 46.5 ml

The following blood volumes will be drawn per subject *not* performing HPA axis assessments:

6 ml for Haematology;

13.5 ml for Biochemistry

12 ml for PK analysis

Total amount of blood drawn per subject, for central analysis: 31.5 ml

Follow-up testing:

A 7.5 ml sample will be collected from subjects requiring additional ACTH challenge testing at FU2 if HPA-axis suppression is observed at Visit 3. A 2.5 ml sample will be collected from subjects at FU1 if laboratory results suggest albumin corrected serum calcium above reference range at the last on-treatment visit.

#### **10.8.4.2 Local Analysis**

A urine pregnancy test will be performed at the trial site at SV2, Visit 3 and 5, and, if applicable, at FU2, in female subjects of child-bearing potential. The test kits will be provided by the Central Laboratory.

#### **10.8.5 Adverse Events**

*Any untoward medical occurrence in a patient or clinical investigation subject administered a pharmaceutical product and which does not necessarily have a causal relationship with this treatment. An adverse event (AE) can therefore be any unfavourable and unintended sign (including an abnormal laboratory finding), symptom, or disease temporally associated with the use of a medicinal (investigational) product, whether or not related to the medicinal (investigational) product. (ICH Harmonized Tripartite Guideline for Good Clinical Practice, E6 (R1)).*

A Serious Adverse Event (SAE) is any untoward medical occurrence that

- results in death
- is life-threatening

- requires inpatient hospitalisation or prolongation of existing hospitalisation
  - results in persistent or significant disability/incapacity
  - is a congenital anomaly/birth defect
- or
- other medically important conditions\*)

\*) Events that may not be immediately life-threatening or result in death or hospitalisation but may jeopardise the subject or may require intervention to prevent one of the other outcomes listed in the definition above. Examples of such events are allergic bronchospasm, blood dyscrasias and convulsions.

Global Pharmacovigilance, LEO Pharma A/S is responsible for the assessment of headquarter expectedness according to LEO Pharma A/S procedures. The relevant reference document for this clinical trial is Investigator's Brochure, edition 12 and subsequent updates as agreed between the head of Medical Department, and the medical director, Global Pharmacovigilance, LEO Pharma A/S.

At all visits, the subject will be asked a non-leading question by the investigator: "How have you felt since I saw you last?" No specific symptoms will be asked for.

If there are no AEs to record, no further questions will be asked and "NO" should be stated. In case there are one or more AEs to record, "YES" should be stated and the investigator will record the event term, intensity, duration, suspected causal relationship to the investigational product and outcome.

It is important that the investigator also observes the subject for any changes not reported by the subject and records these changes.

Only medically qualified personnel must assess AEs.

#### **10.8.5.1 Reporting of Adverse Events**

Events reported by the subject or observed by the (sub)investigator and that fall into any of the above definitions must be recorded on the adverse event page of the CRF and should be described in the following manner:

The **nature** of the event will be described in precise English medical terminology (i.e. not necessarily the exact words used by the subject). Whenever possible, a specific diagnosis should be stated (e.g. allergic contact dermatitis).

For cutaneous adverse events the **location** must be part of the adverse event description and may be described as either the *face, scalp or trunk/limbs*. Additionally, the location will be described using the following terminology:

- *lesional/perilesional* ( $\leq 2$  cm from the border of lesion(s) treated with investigational product) or
- *distant* ( $>2$  cm from the lesion border)

The **intensity** of the event will be described in terms of mild, moderate or severe according to the investigator's clinical judgement.

- **Mild:** The adverse event does not interfere in a significant manner with the subject's normal functioning level and requires no medical intervention.
- **Moderate:** The adverse event interferes with the subject's normal functioning level and may or may not require medical intervention.
- **Severe:** The adverse event produces significant impairment of the subject's functioning or requires medical intervention.

The **duration** of the event will be reported as the start date and stop date of the event.

The **causal relation** of the event to the use of the investigational product will be described in terms of probable, possible, not related or not assessable according to the following:

#### **Probably related**

- Follows a reasonable temporal sequence from administration of the investigational product
- Could not be reasonably explained by the subject's clinical state, environmental or toxic factors or other therapies administered to the subject
- Follows a known pattern of response to the investigational product
- Disappears or decreases on cessation or reduction in dose of the investigational product
- Reappears or worsens upon re-challenge

#### **Possibly related**

- Follows a reasonable temporal sequence from administration of the investigational product

- Could also be reasonably explained by the subject's clinical state, environmental or toxic factors or other therapies administered to the subject
- Follows a known pattern of response to the investigational product

#### **Not related**

- Does not follow a reasonable temporal sequence from administration of the investigational product
- Is better explained by other factors like the subject's clinical state, environmental or toxic factors or other therapies administered to the subject
- Does not follow a known pattern of response to the investigational product

#### **Not assessable**

- The adverse event cannot yet be judged otherwise because present information is insufficient or contradictory. A final assessment (i.e. probably, possibly or not related) shall be made as more information becomes available, at the latest when the subject has completed the trial.

The **outcome** of the event will be classified and handled as follows:

Recovered/resolved	The event has stopped. The stop date of the event must be recorded.
Recovering/resolving	The subject is clearly recovering from an event. The event is, however, not yet completely resolved. Follow-up on the event is required until final outcome is established.
Not recovered/not resolved	Event is still ongoing. Follow-up on the event is required until final outcome is established.
Recovered with sequelae	The event has reached a state where no further changes are expected and the residual symptoms are assumed to persist. An example is hemiparesis after stroke. The stop date of the event must be recorded.
Fatal	The subject has died as a consequence of the event. Date of death is recorded as stop date for the adverse event.

SAEs must be reported on the adverse event form of the CRF book. Additionally reports must be made using the paper Serious Adverse Event Form – Clinical Trial, supplied by LEO Pharma A/S. Apart from the assessment of the intensity, causal relationship to the investigational product(s) and/or trial procedures, the action taken and the outcome to date, this report must contain a comprehensive narrative description of the course of the event.

The completed Serious Adverse Event Form – Clinical Trial must be faxed or scanned and e-mailed to the following local LEO Pharma A/S affiliates:

*For sites in Australia and New Zealand:*

LEO Pharma Pty Ltd:      [contact]      email: [[contact]](mailto:[contact])

*For sites in Canada:*

LEO Pharma Inc.:      [contact]      email: [[contact]](mailto:[contact])

*For sites in France:*

LEO Pharma:      Fax: [name]      email: [[contact]](mailto:[contact])

*For sites in Germany:*

LEO Pharma GmbH:      [contact]      email: [[contact]](mailto:[contact])

*For sites in the United Kingdom:*

LEO Pharma:      [contact]      email: [[contact]](mailto:[contact])

*For sites in the U.S.:*

LEO Pharma Inc.:      [contact]      email: [[contact]](mailto:[contact])

All other relevant reports of diagnostic procedures, hospital records, autopsy reports etc. must be included, as applicable or upon request from Global Pharmacovigilance.

The IRB(s)/IEC(s), regulatory authorities and concerned investigators will be notified of SAEs according to current regulation and local requirements.

All Suspected, Unexpected Serious Adverse Reactions (SUSARs) are subject to expedited reporting to regulatory authorities.

SAEs must be followed indefinitely until a final outcome has been established, i.e. the follow-up may continue beyond the end of the clinical trial.

### 10.8.7 Source Data

**Source data:** *All information in original records and certified copies of original records of clinical findings, observations, or other activities in a clinical trial necessary for the reconstruction and evaluation of the trial. Source data are contained in source documents (original records or certified copies). (ICH E6, 1.51).*

**Source documents:** *Original documents, data, and records (e.g., hospital records, clinical and office charts, laboratory notes, memoranda, subjects diaries or evaluation checklists, pharmacy dispensing records, recorded data from automated instruments, copies or transcriptions certified after verification as being accurate copies, microfiches, photographic negatives, microfilm or magnetic media, x-rays, subject files, and records kept at the pharmacy, at the laboratories and at medico-technical departments involved in the clinical trial). (ICH E6, 1.52).*

Source Data Verification (SDV) is a key function in assuring the sponsor that clinical trial information is recorded and handled in a way that allows its accurate reporting, interpretation and verification. Monitors will, during the conduct of the clinical trial, perform SDV to confirm the accuracy and completeness of CRFs by verifying selected (as specified below) data recorded in the CRF against data recorded in source documents to ensure such records are consistent.

To enable SDV, it is essential that what constitutes source data/documents (see definition above) for the clinical trial data to be collected in the CRF as well as where such data can be found at the trial site is established and agreed with the investigator at each trial site and documented prior to initiation of the clinical trial.

Source data cannot be entered directly into the CRF. Source data should as a general rule be recorded in the subject's medical record or other defined document normally used at the trial site. Source data may be entered on a worksheet only if the clinical trial requires capture of data, which are normally not part of the subject's medical record.

For this clinical trial, the following parameters collected in the CRF should be verifiable from source documents available at the trial site:

- Date of trial visits and date leaving the clinical trial
- Relevant medical history and diagnosis

- Nature of contraception used by the subject and result of pregnancy test(s), when applicable
- Data for evaluation of eligibility criteria
- Dispensation/administration of investigational product
- Concomitant medication (including changes) and diagnoses
- Subject demographics (sex, date of birth)
- Adverse events, (nature, dates)

In addition to the above, the following should be added to the subject's medical record in chronological order, i.e. when these are allocated to the subject:

- Date(s) of conducting the informed consent process including date of provision of subject information
- Date of enrolment
- CRF book number
- The fact that the subject is participating in a clinical trial in psoriasis with a treatment arm of calcipotriol 50 mcg/g plus betamethasone 0.5 mg/g gel for up to 8 weeks.

After un-blinding the clinical trial, the investigators will be notified of the actual treatment allocation and be asked to record this in the subject's medical record.

## **10.9 Safety Evaluation**

### **10.9.1 Primary Response Criteria**

- Adverse drug reactions (ADRs)
- Subjects with serum cortisol concentration of  $\leq 18$  mcg/dl at 30 minutes after ACTH-challenge at Week 4 and at Week 8
- Change in albumin-corrected serum calcium from baseline (SV2) to Week 4, Week 8, and end of treatment
- Change in 24-hour urinary calcium excretion from baseline (SV2) to Week 4, Week 8, and end of treatment

### **10.9.2 Secondary Response Criteria**

- Adverse events (AEs)
- Subjects with serum cortisol concentration of  $\leq 18$  mcg/dl at both 30 and 60 minutes after ACTH-challenge at Week 4 and at Week 8

- Change in urinary calcium:creatinine ratio from baseline (SV2) to Week 4 and Week 8

### **10.9.3 Evaluation of (Serious) Adverse Events**

Refer to Section [10.9.1](#) and [10.9.2](#).

### **10.9.4 Evaluation of Laboratory Data**

Refer to Section [10.9.1](#). and [10.9.2](#).

### **10.9.5 Evaluation of Other Observations**

- PK evaluation

## **10.10 Efficacy Evaluation**

### **10.10.1 Secondary Response Criteria**

- Subjects with “Controlled disease” (i.e., “Clear” or “Almost clear”) according to the investigator’s global assessment of disease severity on the body at end of treatment.
- Percentage change in PASI from baseline to end of treatment.
- Subjects with “Controlled disease” (i.e., “Clear” or “Very mild”) according to the patient’s global assessment of disease severity on the body at end of treatment.

## **10.11 Statistical Analysis**

### **10.11.1 Subject Qualification for Analysis**

All subjects enrolled into the trial (i.e., signed informed consent obtained and a CRF number assigned) will be accounted for in the clinical study report.

All subjects who apply any IP will be included in the full analysis set and analysed for efficacy. Exclusion from the full analysis set will be carefully considered for subjects who apply no IP or who provide no efficacy data following start of treatment.

All subjects who apply any IP and for whom the presence or confirmed absence of adverse events is available will be included in the safety analysis set and analysed for safety, except the analysis of the results from the ACTH-challenge test.

For the analysis of the results from the ACTH-challenge test a per protocol analysis set will be defined by including the subjects performing HPA axis assessments from the full analysis set, however excluding the subjects who do not:

- apply any IP

- meet the inclusion criterion concerning evidence of adrenal function at baseline
- provide any results for the ACTH-challenge test after receiving IP

The decisions regarding inclusion/exclusion of subjects and/or subject data from the trial analysis sets will be documented in the clinical study report.

### **10.11.2 Reasons for Leaving the Trial**

The reasons for leaving the trial will be presented separately for subjects who apply any IP and for enrolled subjects not assigned to treatment.

### **10.11.3 Baseline Characteristics**

Descriptive statistics of demographics and other baseline characteristics will be presented for all subjects in the safety analysis set and per protocol analysis set as these are the datasets used for primary response criteria.

Demographics include age, sex, ethnicity, race and skin type. Other baseline characteristics include duration of psoriasis vulgaris, physical examination, investigator's global assessment of disease severity on body, PASI (calculated from the investigator's assessment of extent and severity of the clinical signs), investigator's assessment of extent of psoriasis (BSA and scalp), patient's global assessment of disease severity on body, concomitant medication and concurrent diagnoses.

Age and sex will also be presented by centre.

### **10.11.4 Compliance**

Compliance with treatment instructions will be tabulated for all subjects who apply any IP.

The number and percentage of subjects who comply and who do not comply with the trial treatment regimen will be summarised. The extent of non-compliance as categories of the percentage of applications missed (e.g.  $\leq 10\%$ ,  $> 10$  to  $20\%$ , etc.) will also be presented.

### **10.11.5 Analysis of Safety**

The analysis of safety will be based on the safety analysis set according to the defined response criteria, except the analysis of the results from the ACTH-challenge test which will be based on the per protocol analysis set.

#### **10.11.5.1 Adverse Events**

Adverse events will be coded in accordance with the current version of the MedDRA dictionary.

All adverse events recorded during the course of the trial will be included in the subject data listings. An event will be considered emergent with the trial treatment if it started after the first application of the investigational product or if it started before this and increased in intensity after the first application of investigational product. The tabulations described below will only include the events that are emergent with the trial treatment.

The number of subjects experiencing each type of adverse event (according to MedDRA Preferred Terms within Primary System Organ Class) will be tabulated regardless of the number of times each adverse event is reported by each subject.

An overview summary of the number of subjects with any adverse events, adverse drug reactions, lesional/perilesional adverse events, serious adverse events and adverse events leading to withdrawal from the trial will be produced.

The causal relationship to IP for each type of adverse event (according to the Preferred Term) will be tabulated. Where there are several recordings of causal relationship to IP for a given type of adverse event, causal relationship will be taken as the most-related recording from the last report of that adverse event, since that is when the investigator will be in possession of most information and so best able to judge causal relationship.

The intensity for each type of adverse event (according to the Preferred Term) will be presented. Where there are several recordings of intensity for a given type of adverse event the most severe intensity will be selected.

Adverse drug reactions are defined as adverse events for which the investigator has not described the causal relationship to IP as “not related”. The number of subjects experiencing each type of adverse drug reaction (according to the Preferred Term) will be tabulated. The intensity for each type of adverse drug reaction will be presented.

The number of subjects experiencing each type of lesional/perilesional adverse event, lesional/perilesional adverse event on the body and lesional/perilesional adverse event on the scalp (according to the Preferred Term) will be tabulated.

Serious adverse events and adverse events leading to withdrawal from the trial will be evaluated separately, and a narrative for each will be given.

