Table 3-34 Adverse events by MedDRA primary system organ class and preferred term: safety analysis set

Table 3-35 Intensity of adverse events by MedDRA primary system organ class and preferred term: safety analysis set

Table 3-36 Causal relationship of adverse events to IMP by MedDRA primary system organ class and preferred term: safety analysis set

Table 3-37 Adverse drug reactions by MedDRA primary system organ class and preferred term: safety analysis set

Table 3-38 Intensity of adverse drug reactions by MedDRA primary system organ class and preferred term: safety analysis set

Table 3-39 Lesional/perilesional adverse events by MedDRA primary system organ class and preferred term: safety analysis set

Table 3-40 Lesional/perilesional adverse events on the body by MedDRA primary system organ class and preferred term: safety analysis set

Table 3-41 Lesional/perilesional adverse events on the scalp by MedDRA primary system organ class and preferred term: safety analysis set

Table 3-42 Adverse events by age group, MedDRA primary system organ class and preferred term: safety analysis set

Table 3-43 Adverse events by sex, MedDRA primary system organ class and preferred term: safety analysis set

Table 3-44 Adverse events by race, MedDRA primary system organ class and preferred term: safety analysis set

Table 3-45 Adverse events by baseline IGA on the body, MedDRA primary system organ class and preferred term: safety analysis set

Table 3-46 Adverse events by baseline total extent of psoriasis, MedDRA primary system organ class and preferred term: safety analysis set

Table 3-47 Adverse events by IMP usage (<40 g/week, ≥ 40 g/week), MedDRA primary system organ class and preferred term: safety analysis set

Table 3-48 Systolic blood pressure by visit: safety analysis set

Table 3-49 Change in systolic blood pressure from baseline to Week 4 and Week 8: safety analysis set

Table 3-50 Diastolic blood pressure by visit: safety analysis set

Table 3-51 Change in diastolic blood pressure from baseline to Week 4 and Week 8: safety analysis set

Table 3-52 Heart rate by visit: safety analysis set

Table 3-53 Change in heart rate from baseline to Week 4 and Week 8: safety analysis set

Patient Data Listings (Appendix 1)

1-7 Subjects Receiving Investigational Product from Specific Batches

Patient Data Listings (Appendix 2)

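### Causality is set per Preferred Term from the last report only, so the causality table can understate relatedness and disagree with the adverse drug reaction table

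*Protocol*

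**What the plan says.** Protocol 10.11.5.1 plans a causality table: "The causal relationship to IP for each type of adverse event (according to the Preferred Term) will be tabulated". The rule for repeats begins "Where there are several recordings of causal relationship to IP for a given type of adverse event" and continues "causal relationship will be taken as the most-related recording from the last report of that adverse event". The reason given is "since that is when the investigator will be in possession of most information and so best able to judge causal relationship".

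The next paragraph treats intensity differently: "Where there are several recordings of intensity for a given type of adverse event the most severe intensity will be selected".

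A separate paragraph covers adverse drug reactions (ADRs): "Adverse drug reactions are defined as adverse events for which the investigator has not described the causal relationship to IP as" *not related*. It does not mention the last-report rule. ADRs are the first item in the primary response criteria (Protocol 10.9.1).

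SAP 6.4.3 refers adverse events back to the protocol and adds event counts wherever subject counts are shown. It sets no causality rule of its own. SAP Appendix I lists Table 3-36 ("Causal relationship of adverse events to IMP by MedDRA primary system organ class and preferred term"), Table 3-37 (ADRs) and Table 3-38 (intensity of ADRs) as separate outputs. Neither document defines a report, or says whether the last-report rule reaches Tables 3-37 and 3-38.

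**The concern.** The stated reason holds for one episode followed over time, because the investigator's last judgement on it is the best informed. It does not carry over to two different episodes. What is learned about an episode in Week 7 says nothing new about one in Week 2. A subject with probably related pruritus in Week 2 and unrelated pruritus in Week 7 would appear in Table 3-36 as *not related*.

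The design makes such mixed sequences plausible:

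- Subjects found clear at Visit 2 or Visit 4 stop applying the gel but stay in the trial, and restart if psoriasis returns (Protocol 10.1, Treatment Period).
- Causality is judged partly on timing, on what happens at cessation and on re-challenge (Protocol 10.8.5.1), so episodes on and off treatment can properly be judged differently.
- Other topical products are allowed on the face and sensitive areas (Protocol 10.6.10), so a similar reaction may have another cause.

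Safety is the primary objective. At stake is whether the causality table shows all the relatedness that was recorded, and whether it agrees with the ADR table.

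**Working it through.** **1. The plan's own figure.** Protocol 10.3 gives an upper limit of about 4% for an exact two-sided 95% interval when 0 of 100 subjects have an event. Check: 1 − 0.025^(1/100) = 0.0362, or 3.62%. It reproduces.

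**2. What the rule pools.** It operates on a type of adverse event, and the sentence introducing the table defines type by Preferred Term. It then picks the most-related recording within the last report. The final assessment of a single event would normally carry one causality, so the choice makes sense mainly if several entries under a term are pooled. As written, separate episodes under one term are collapsed.

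**3. The rule applied to two episodes under one term in one subject.**

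| Sequence | Last-report rule | Most-related rule | ADR, event by event |
|---|---|---|---|
| possible, then not related | not related | possible | yes |
| probable, then not related | not related | probable | yes |
| not related, then possible | possible | possible | yes |

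**4. Direction.** The last report is a subset of all reports. The maximum over a subset cannot exceed the maximum over the whole, so the last-report rule gives the same relatedness as the most-related rule or a lower one, never a higher one.

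**5. Consequence for the ADR table.** There are two possibilities, and for a given subject they exclude each other.

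- *ADRs taken event by event* (the literal definition): the earlier related episode is an ADR and the subject counts in Table 3-37. Table 3-36 shows the same subject as *not related* for that term. The primary count is intact, and the two tables disagree.
- *ADRs taken from the type-level result* (stated nowhere): both tables lose the related episode. They agree, and the primary count is too low.

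Table 3-38 has a related gap. The text does not say whether the intensity shown is that of the related episode or the worst of any episode under the term.

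**6. Size, as an illustration only.** The documents give no count of subjects with mixed causality under one term. Assume that one subject is affected, that nobody else has that reaction, and that the second possibility in step 5 applies. Clopper-Pearson 95% limits, with the upper limit as the 0.975 quantile of Beta(x + 1, n − x):

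| Subjects with the reaction | Upper limit, n = 100 |
|---|---|
| 0 (related episode lost) | 3.62% |
| 1 (kept) | 5.45% |
| 2 (kept) | 7.04% |
| 3 (kept) | 8.52% |

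With the 107 treated subjects in SAP Table 3, the limits for 0 and 1 are 3.39% and 5.10%. No confidence interval is planned for ADRs, so these figures describe precision and do not correspond to any planned output.

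**The case against.** A reader might infer that the rule removes drug-related events from the primary ADR result. The documents do not support that. The rule stands in the paragraph on the causality table. ADRs are defined afterwards and independently, by what the investigator recorded for the event. Nor do the events disappear: the protocol puts all of them in the subject listings (Listing 7-5 in the SAP). This objection stands, and it confines the established defect to Table 3-36 and its agreement with Table 3-37.

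A narrower reading of the rule is also available. The appeal to accumulating information fits successive assessments of one event, and Protocol 10.8.5.1 has just such a process: an event first called not assessable receives a final judgement later, and unresolved events are followed to outcome. If report means only that, separate episodes are not governed by the rule at all. The reading is possible, but the opening clause speaks of an event type, and the most-related selection presupposes pooling. Even on this reading the plan would lack a rule for separate episodes.

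The contrast with intensity is not an error in itself. Peak intensity is a maximum of observed states, whereas causality is a judgement that may be revised. That defends a last-judgement rule within an episode, but not across episodes.

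Finally, the SAP refers to consolidated protocol versions 4.0 and 6.0, while the protocol supplied carries the eligibility criteria that the SAP shows as replaced. The adverse event wording of the later versions cannot be checked here. The SAP's table of relevant amendments lists no change to it.

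**Conclusion.** The point holds for the causality table. As written, a later *not related* episode overrides an earlier related one under the same Preferred Term, and against a most-related rule the shift can only be downward. On the literal ADR definition, Table 3-37 keeps the subject and the two tables then conflict. A shortfall in the primary ADR count is conditional on the type-level rule also being applied there, which neither document says.

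The size is unknown. It depends on how many subjects had a related episode followed by an unrelated one under the same term, and this may be none. No sample-size or power figure is affected. The conclusion rests on reading a report as covering separate episodes under a term, which is the more natural reading but is not defined, and on the later protocol versions having kept this text. It is a modest correction, worth making because safety is the primary objective and with sparse events one subject can decide whether a reaction is shown as related.

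**What to change.** Replace the single rule with three statements:

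1. Within one episode, causality is the investigator's last assessment.
2. Across separate episodes of the same Preferred Term in a subject, Table 3-36 shows the most-related causality. State where not assessable ranks.
3. Tables 3-37 and 3-38 are derived from episode-level causality: a subject counts for a term if any episode is classed other than *not related*, and intensity in Table 3-38 comes from those episodes.

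The SAP says that it was prepared after review of the data, so the change should be recorded as such in the trial report, with the number of subjects whose classification differs between the two rules.

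The cost is one or two sentences and minor programming on data already collected. The downside is a possibly slightly higher count of related events in Table 3-36.
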